6.3.2. Group B

The following procedures will be conducted during the Phase 1b and Phase 2 Safety run-in Lead-in (Cycle 0) on Days 1, 8, and 14 (unless otherwise specified).

- ENTO will be administered orally every 12 hours on Days 1-14 as a single agent
 - Review prior/concomitant medication
 - Record any adverse events
 - Vital signs; including blood pressure, respiratory rate, pulse, temperature, oxygen saturation level
 - Complete physical examination (Day 1)
 - Obtain current smoking status (Day 1)
 - CCI [REDACTED]
 - ECOG performance status (Day 1)
 - Urine pregnancy test (negative pregnancy test required for all female subjects unless surgically sterile or menopausal prior to dose on Day 1)
 - Obtain blood samples for:
 - Chemistry (Days 1, 8, and 14)
 - Hematology (Days 1, 8, and 14)
 - Coagulation (Day 14 only)
 - PK (Days 1, 8, and 14 at pre-dose and 2 hours post-dose of ENTO)
 - Biomarkers (Days 1, 8, and 14 at pre-dose)
- Note:** ENTO should be held until the pre-dose blood samples have been drawn. Record approximate times of the last 2 doses of ENTO on PK collection days and the time the PK blood samples are obtained.
- A bone marrow aspirate sample for disease assessment and biomarker research will be collected at the end of the monotherapy lead-in period (ie, Cycle 0 Day 14 or after the minimum 5 days of ENTO), and prior to initiating therapy with hypomethylating agent. Biopsy will be used in the event the aspirate cannot be collected or analyzed (eg, dry-tap, hemodiluted specimen, or lack of spicules).
 - Subjects with cytogenetic and molecular mutations at screening must have cytogenetic and molecular mutation testing repeated at subsequent bone marrow examinations (Cycle 0 Day 14, Cycle 1 Day 28, count recovery, End of Study).

The following procedures will be conducted during the Phase 2 Randomization Lead-in (Cycle 0) on Days 1 and 5 (unless otherwise specified).

- ENTO will be administered orally every 12 hours on Days 1-5 as a single agent
 - Review prior/concomitant medication
 - Record any adverse events
 - Vital signs; including blood pressure, respiratory rate, pulse, temperature, oxygen saturation level
 - Complete physical examination (Day 1)
 - Obtain current smoking status (Day 1)
 - CCI [REDACTED]
 - ECOG performance status (Day 1)
 - Urine pregnancy test (negative pregnancy test required for all female subjects unless surgically sterile or menopausal prior to dose on Day 1)
 - Obtain blood samples for:
 - Chemistry (Days 1 and 5)
 - Hematology (Days 1 and 5)
 - Coagulation (Day 5 only)
 - PK (Days 1 and 5 at pre-dose and 2 hours post-dose of ENTO)
 - Biomarkers (Days 1 and 5 at pre-dose)
- Note:** ENTO should be held until the pre-dose blood samples have been drawn. Record approximate times of the last 2 doses of ENTO on PK collection days and the time the PK blood samples are obtained.
- If circulating blasts have cleared at the end of monotherapy lead-in (Cycle 0 Day 5), then a bone marrow aspirate sample will be performed for disease assessment. Biopsy will be used in the event the aspirate cannot be collected or analyzed (eg, dry-tap, hemodiluted specimen, or lack of spicules).
 - Subjects with cytogenetic and molecular mutations at screening must have cytogenetic and molecular mutation testing repeated at subsequent bone marrow examinations (Cycle 0 Day 5, Cycle 1 Day 28, count recovery, End of Study).

The following procedures will be conducted on Days 1, 8, and 28 of induction Cycles 1-4 (unless otherwise specified).

- ENTO will continue to be administered orally every 12 hours on Days 1-28 in combination with IV decitabine 20 mg/m² daily on Days 1-10 or IV/SC azacitidine 75mg/m² daily on Days 1-7 of each 28-day cycle. Subjects enrolled in the Phase 2 safety run-in will only receive ENTO in combination with azacitidine. Subjects enrolled in Phase 2 randomization will receive ENTO in combination with decitabine or azacitidine. Subjects will receive at least 2 cycles of induction therapy but no more than 4 cycles.
- Review prior/concomitant medication
- Record any adverse events
- Vital signs; including blood pressure, respiratory rate, pulse, temperature, oxygen saturation level (Days 1 and 8 of each cycle)
- Weight (Day 1 of each cycle)
- ECOG performance status (Day 1 of each cycle)
- Physical exam (Day 1 of each cycle)
- Obtain smoking status for past 28 days (Day 1 of each cycle)
- Urine pregnancy test (for all female subjects unless surgically sterile or menopausal prior to dose on Day 1)
- Obtain blood samples for:
 - Chemistry (Days 8 and 28 of each cycle)
 - Hematology (Days 8 and 28 of each cycle)
 - Coagulation (Day 8 of each cycle)
 - PK (Cycle 1 Day 8 at pre-dose, 2 hours, and 4 hours post-dose of ENTO; Day 8 of subsequent cycles at pre-dose and 2 hours post-dose of ENTO; Day 28 of every cycle at pre-dose and 2 hours post-dose of ENTO)
 - Biomarkers (Cycle 1 Days 8 and 28 at pre-dose)

Note: ENTO should be held until the pre-dose blood samples have been drawn. Record approximate times of the last 2 doses of ENTO on PK collection days and the time the PK blood samples are obtained.

- Obtain bone marrow aspirate and biopsy samples at the end of every 2 cycles (Cycle 2 Day 28 and Cycle 4 Day 28) or as clinically indicated for disease assessment and biomarker research. If the bone marrow is consistent with Morphologic CR or CRi status per [Appendix 5](#), then evaluate MRD as per institutional practice and [Appendix 7](#). Biopsy will be used in the event the aspirate cannot be collected or analyzed (eg, dry-tap, hemodiluted specimen, or lack of spicules).
 - If the subject achieves <5% blasts by morphology and flow cytometry or has evidence of clinical benefit after completing 2-4 induction cycles but is not eligible for SCT, the subject will have the option to receive maintenance therapy with ENTO in combination with decitabine or azacitidine. Subjects with persistent evidence of disease (ie, blasts \geq 5%) after Cycle 2 may receive up to 2 more induction cycles until subject achieves <5% blasts.

If <5% blasts by morphology and flow cytometry is not achieved or the subject does not show evidence of clinical benefit after 2-4 induction cycles, the subject is considered a treatment failure and will have met study efficacy endpoint criteria, but will remain on study for required study-related follow-up procedures.

The following procedures will be conducted on Days 1 and 28 of each 28-day cycle of Entospletinib + Hypomethylating agent Maintenance Therapy.

- ENTO will be administered orally every 12 hours on Days 1-28 in combination with IV decitabine 20 mg/m² daily on Days 1-5 or IV/SC azacitidine 75mg/m² daily on Days 1-7 of each cycle for at least 2 cycles. Subjects enrolled in the safety run-in will only receive ENTO in combination with azacitidine.
 - After completing at least 2 cycles, the subject may proceed to SCT. If not eligible for SCT, subjects will have the option to continue on maintenance therapy with ENTO in combination with the assigned hypomethylating agent. Subjects who are intolerant of the hypomethylating agent may switch to ENTO monotherapy maintenance at any time after completing the first 2 cycles. Maintenance may continue as long as the subject is experiencing benefit and does not meet the criteria for study treatment discontinuation.
- Review prior/concomitant medication
- Record any adverse events
- Vital signs; including blood pressure, respiratory rate, pulse, temperature, oxygen saturation level (Day 1 of each cycle)
- Physical exam (Day 1 of each cycle)
- Obtain smoking status for past 28 days (Day 1 of each cycle)
- Urine pregnancy test (for all female subjects unless surgically sterile or menopausal prior to dose on Day 1)

- Obtain blood samples on Day 28 of each cycle:
 - Chemistry
 - Hematology
 - PK (pre-dose and 2 hours post-dose of ENTO)

Note: ENTO should be held until the pre-dose blood samples have been drawn. Record approximate times of the last 2 doses of ENTO on PK collection days and the time the PK blood samples are obtained.

- Obtain a bone marrow aspirate for disease assessment and biomarker research at the end of every 4 cycles on Day 28 (eg, Cycle 4 Day 28, Cycle 8 Day 28) or as clinically indicated. Subjects who achieve CR/CRi that is stable for 2 consecutive bone marrow evaluations are not required to have further bone marrow aspirate samples collected, unless clinically indicated. Biopsy will be used in the event the aspirate cannot be collected or analyzed (eg, dry-tap, hemodiluted specimen, or lack of spicules).

The following procedures will be conducted on Days 1 and 28 of each 28-day cycle of Entospletinib Maintenance Therapy.

- ENTO will be administered orally every 12 hours as a single agent on Days 1-28 and may continue up to 12 cycles as long as the subject is experiencing benefit and does not meet the criteria for study treatment discontinuation. Extension of maintenance may occur on an individual basis if approved by the Principal Investigator.
- Review prior/concomitant medication
- Record any adverse events
- Vital signs; including blood pressure, respiratory rate, pulse, temperature, oxygen saturation level (Day 1 of each cycle)
- Physical exam (Day 1 of each cycle)
- Obtain smoking status for past 28 days (Day 1 of each cycle)
- Urine pregnancy test (for all female subjects unless surgically sterile or menopausal prior to dose on Day 1)
- Obtain blood samples on Day 28 of each cycle:
 - Chemistry
 - Hematology
 - PK (pre-dose and 2 hours post-dose of ENTO)

Note: ENTO should be held until the pre-dose blood samples have been drawn. Record approximate times of the last 2 doses of ENTO on PK collection days and the time the PK blood samples are obtained.

- Obtain a bone marrow aspirate for disease assessment and biomarker research at the end of every 4 cycles on Day 28 (eg, Cycle 4 Day 28, Cycle 8 Day 28) or as clinically indicated. Subjects who achieve CR/CRi that is stable for 2 consecutive bone marrow evaluations are not required to have further bone marrow aspirate samples collected, unless clinically indicated. Biopsy will be used in the event the aspirate cannot be collected or analyzed (eg, dry-tap, hemodiluted specimen, or lack of spicules).

The following procedures will be conducted at Remission/Relapse.

- Obtain blood samples for:
 - Chemistry
 - Hematology
 - Biomarkers
- Obtain bone marrow aspirate samples for disease assessment and biomarker testing. Biopsy will be used in the event the aspirate cannot be collected or analyzed (eg, dry-tap, hemodiluted specimen, or lack of spicules). Subjects who achieve CR/CRi that is stable for 2 consecutive bone marrow evaluations are not required to have further bone marrow aspirate samples collected, unless clinically indicated.

6.3.3. Group C

The following procedures will be conducted on Days 1, 8, 14, and 28 of each 28-day cycle (unless otherwise specified).

- ENTO will be administered orally every 12 hours on Days 1-28 as a single agent as long as the subject is experiencing benefit and does not meet criteria for study treatment discontinuation.
- Review prior/concomitant medication
- Record any adverse events
- Vital signs; including blood pressure, respiratory rate, pulse, temperature, oxygen saturation level (Day 1 of each cycle and Cycle 1 Days 8, 14, and 28)
- Weight (Day 1 of each cycle)
- ECOG performance status (Day 1 of each cycle and Cycle 1 Day 14)
- Physical exam (Day 1 of each cycle and Cycle 1 Day 14)

- Obtain smoking status for past 28 days (Day 1 of each cycle)
- **CCI**
- Urine pregnancy test (negative pregnancy test required for all female subjects unless surgically sterile or menopausal prior to dose on Day 1)
- Obtain blood samples for:
 - Chemistry (Cycle 1 Days 1, 8, 14, and 28; Days 1 and 28 of each subsequent cycle)
 - Hematology (Cycle 1 Days 1, 8, 14, and 28; Days 1 and 28 of each subsequent cycle)
 - Coagulation (Day 1 of each cycle)
 - PK (Cycle 1 Days 1, 8, 14, and 28; Day 28 of each subsequent cycle at pre-dose and 2 hours post-dose of ENTO)
 - Biomarkers (Cycle 1 Days 1, 8, 14, and 28 at pre-dose)
 - **Phase 1b only:** For subjects dosed with 400 mg and 800 mg ENTO, pharmacodynamic (BAT assay) samples will be collected (Cycle 1 Days 1, 8, 14, and 28 at pre-dose and 2 hours post-dose of ENTO). BAT assay samples may also be collected at pre-dose on Day 28 of subsequent cycles during the escalation phase.

Note: ENTO should be held until the pre-dose blood samples have been drawn. Record approximate times of the last 2 doses of ENTO on PK collection days and the time the PK blood samples are obtained.

- Obtain a bone marrow aspirate and biopsy on Day 28 of Cycles 1 and 2 for disease assessment and biomarker testing. If the bone marrow is consistent with Morphologic CR or CRi status per [Appendix 5](#), then evaluate MRD as per institutional practice and [Appendix 7](#).
- Obtain a bone marrow aspirate sample for disease assessment and biomarker testing every 4 cycles beginning on Cycle 4 Day 28 of subsequent cycles (eg, Cycle 4 Day 28, Cycle 8 Day 28) or as clinically indicated. Subjects who achieve CR/CRi that is stable for 2 consecutive bone marrow evaluations are not required to have further bone marrow aspirate samples collected, unless clinically indicated. Biopsy will be used in the event the aspirate cannot be collected or analyzed (eg, dry-tap, hemodiluted specimen, or lack of spicules).

The following procedures will be conducted at Remission/Relapse.

- Obtain blood samples for:
 - Chemistry
 - Hematology
 - Biomarkers

- Obtain bone marrow aspirate samples for disease assessment and biomarker testing. Biopsy will be used in the event the aspirate cannot be collected or analyzed (eg, dry-tap, hemodiluted specimen, or lack of spicules). Subjects who achieve CR/CRi that is stable for 2 consecutive bone marrow evaluations are not required to have further bone marrow aspirate samples collected, unless clinically indicated.

6.4. Assessments for Premature Discontinuation from Study

If a subject discontinues study treatment (eg, as a result of an AE), every attempt should be made to keep the subject in the study to perform the required study-related follow-up and procedures. If this is not possible or acceptable to the subject or investigator, the subject may be withdrawn from the study.

6.4.1. Criteria for Discontinuation of Study Treatment

Study treatment may be discontinued in the following instances:

- Intercurrent illness that would, in the judgment of the investigator, affect assessments of clinical status to a significant degree. Following resolution of intercurrent illness, the subject may resume study dosing at the discretion of the investigator.
- Unacceptable toxicity, or toxicity that, in the judgment of the investigator, compromises the ability to continue study-specific procedures or is considered to not be in the subject's best interest
- Group C subjects with the following increases in pre-treatment baseline blast percentage in the bone marrow:
 - < 5% blasts at baseline with an increase to $\geq 10\%$ blasts
 - 5 to 10% blasts at baseline with an increase to $\geq 20\%$ blasts
 - 11 to 20% blasts at baseline with an increase to $\geq 30\%$ blasts
 - **Exception:** Subjects will be allowed to continue therapy for up to 2 cycles. If at the time of the post Cycle 2 disease assessment there has not been an improvement in cytopenias or blast count, peripheral blood or marrow, that would suggest clinical benefit, the subject is to be removed from study. Decisions regarding continuation of therapy in subjects on Group C past Cycle 2 will be reviewed with the PI and Medical Monitor.
- Subjects may be removed in the case of new CNS disease or other new sites of extramedullary involvement
- Groups B and C: requires continued treatment with hydroxyurea after Cycle 1

- Subject request to discontinue for any reason. Subjects who withdraw from the study treatment phase of the study should still be followed for survival until 3 years from study start (see Section 6.5, Long term follow up)
- Subject noncompliance with study treatment administration, study procedures, or study requirements should be withdrawn from study treatment in circumstances that increase risk or substantially compromise the interpretation of study results
- Pregnancy during the study (refer to Appendix 4)
- The investigator, in consultation with the Gilead Sciences Medical Monitor or designee, may withdraw any subject from the study treatment, if, in the investigator's opinion, it is not in the subject's best interest to continue.
- Discontinuation of the study at the request of Gilead, a regulatory agency or an institutional review board or independent ethics committee (IRB/IEC)
- If allowed by local regulations, Gilead Sciences may transition subjects from study treatment to commercial drug supply when ENTO becomes commercially available in the country where the subject is living.

6.4.2. End of Study Treatment

Subjects will be removed from study treatment when any of the criteria listed in Section 6.4.1 apply. The following procedures will be conducted when a subject discontinues study treatment and prior to initiating a new therapy.

- Review prior/concomitant medication
- Record any adverse events
- ECOG performance status
- Physical exam
- Vital signs; including blood pressure, respiratory rate, pulse, temperature, oxygen saturation level
- Weight
- Obtain blood samples for:
 - Chemistry
 - Hematology
 - Coagulation

- Biomarker testing
- **Phase 1b only:** For Group C subjects dosed with 400 mg and 800mg ENTO, a BAT assay sample may be collected
- Obtain bone marrow aspirate and biopsy samples for disease assessment and biomarker testing (if not performed within the last 2 weeks). If the bone marrow is consistent with Morphologic CR or CRi status per [Appendix 5](#), then evaluate MRD as per institutional practice and [Appendix 7](#).
- **CCI** [REDACTED]

6.4.3. 30-day Follow-up

After the last dose of study drug, subjects should be followed for any drug-related AEs and/or ongoing serious adverse events (SAEs) until those events have resolved or become stable, whichever occurs later. The site will contact the study subject regardless of AE/SAE status approximately 30 days after the subject's last dose of study drug to assess adverse events since the last study visit and review concomitant medications. Contact the subject by phone (or in person, if necessary) to assess the subject's condition and record any adverse events reported during the follow-up contact. Document the phone call or visit.

6.5. Long Term Follow-up

Long term follow-up for survival will be conducted every 6 months (\pm 4 weeks) after the End of Study Treatment visit for up to 3 years (since the start of study therapy). Information to be gathered includes leukemia treatments, other malignancies, and survival. This follow-up can be done during a routine clinic visit, other contact with the subject, or via telephone. Gilead reserves the right to discontinue or shorten the duration of participation in the long term follow-up period at any time. See section [9.3.4](#) for details regarding study discontinuation.

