- Vital signs; including blood pressure, respiratory rate, pulse, temperature, oxygen saturation level every 2 cycles (eg, Cycle 1 Day 1, Cycle 3 Day 1)
- Complete physical examination every 2 cycles (eg, Cycle 1 Day 1, Cycle 3 Day 1)
- Obtain smoking status for past 28 days (Day 1 of each cycle)
- ECOG performance status every 2 cycles on Day 28 (eg, Cycle 2 Day 28, Cycle 4 Day 28)
- Urine pregnancy test (for all female subjects unless surgically sterile or menopausal prior to dose on Day 1)
- Obtain blood samples for:
 - Chemistry (every 2 cycles from Cycle 1 Day 28)
 - Hematology (every 2 cycles from Cycle 1 Day 28)
 - Coagulation (every 2 cycles from Cycle 1 Day 28)
 - PK at pre-dose and 2 hours post-dose of ENTO (Day 28 of each cycle)
- Obtain bone marrow aspirate samples for disease assessment and biomarker testing at the end of every 4 cycles on Day 28 (eg, Cycle 4 Day 28, Cycle 8 Day 28, etc.) or as clinically indicated. Biopsy will be used in the event the aspirate cannot be collected or analyzed (eg, dry-tap, hemodiluted specimen, or lack of spicules). Subjects who achieve CR/CRi that is stable for 2 consecutive bone marrow evaluations are not required to have further bone marrow aspirate samples collected, unless clinically indicated.

The following procedures will be conducted at Blood Count Recovery/Remission/Relapse.

- Obtain blood samples for:
 - Chemistry
 - Hematology
 - Biomarkers
- Obtain bone marrow aspirate samples for disease assessment and biomarker testing. Biopsy will be used in the event the aspirate cannot be collected or analyzed (eg, dry-tap, hemodiluted specimen, or lack of spicules). Subjects who achieve CR/CRi that is stable for 2 consecutive bone marrow evaluations are not required to have further bone marrow aspirate samples collected, unless clinically indicated.

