Appendix 2. Study Procedures Tables

Group A: Phase 1b Dose Escalation (Entospletinib + cytarabine + daunorubicin)

Study Phase	Screening	Cycle 0 Entospletinib Lead-in			Cycle 1 (and Cycle 2, if needed) Entospletinib + 7+3				At Blood Count Recovery/ Remission/ Relapse	End of Study Treatment	30-day Follow-up	3-year Long Term Follow-up
		1	8	14	1	3	7	14				
Study Day	Screening	1	8	14	1	3	7	14				
Window (day)	-14	±2	±2	±2	±2	±2	±2	±2	±2	±7	±7	± 4 weeks
General and Safety Assessments												
Informed Consent	X											
Medical & Medication History	X											
Adverse Events/ Concomitant Medications	X	X	X	X	X	X	X	X		X	X	
Physical Exam ^a	X	X			X					X		
Vital Signs ^b	X	X	X	X	X	X	X			X		
Height and Weight ^c	X				X		X			X		
ECG ^d	X											
ECHO/MUGA ^e	X							X				
ECOG Performance Status	X	X						X		X		
Overall survival, leukemia treatments, and other malignancies												X (every 6 months)
X-ray ^m (Investigator's discretion)	X											
Study Treatment												
Entospletinib Administration ^f		X	X	X	X	X	X	X				
IV daunorubicin ^f					X	X						
IV cytarabine ^f					X	X	X					

Study Phase	Screening	Cycle 0 Entospletinib Lead-in			Cycle 1 (and Cycle 2, if needed) Entospletinib + 7+3				At Blood Count Recovery/ Remission/ Relapse	End of Study Treatment	30-day Follow-up	3-year Long Term Follow-up
		1	8	14	1	3	7	14				
Study Day	Screening	1	8	14	1	3	7	14				
Window (day)	-14	±2	±2	±2	±2	±2	±2	±2	±2	±7	±7	± 4 weeks
Laboratory Assessments												
Chemistry ^g	X	X	X	X			X	X	X	X		
Hematology	X	X	X	X			X	X	X	X		
Coagulation	X			X			X	X		X		
Urinalysis	X											
Serum Pregnancy Test and FSH ^h	X											
HIV/HBV/HCV	X											
Bone Marrow Assessments												
Biopsy ^l	X							X	X	X		
Aspirate ^j	X			X				X	X	X		
PK ^k		X	X	X		X	X	X				
Biomarkers ^l		X	X	X			X	X	X	X		

CCI

- a After discharge from the hospital, a focused physical exam may be completed at the Investigator's discretion.
- b Vital signs include measurement of blood pressure, respiratory rate, pulse, temperature, and oxygen saturation level. Vitals signs may be measured daily during hospitalization and at the Investigator's discretion after discharge from the hospital.
- c Height and weight will be measured at Screening. Only weight will be measured on Days 1 and 7 of Cycles 1 and 2 and at End of Study Treatment.
- d ECG is required at Screening and may be performed at the Investigator's discretion following enrollment.

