6.2.2. Analysis of the Secondary Endpoints

Subjects will be considered as treatment failure if having at least one efficacy assessment prior to SCT and other anticancer therapy (excluding SCT and conditioning regimen) but none of these efficacy assessments is CRc, CR, CRi, or PR; date of treatment failure will be the date of last adequate efficacy assessment prior to SCT and other anticancer therapy (excluding SCT and conditioning regimen). The events and censoring rules are detailed in [Table 6-1](#). Of note, other anti-cancer therapy excludes SCT and conditioning regimen in this table, and the criteria are hierarchical: subjects who meet the criteria on the top will be excluded from the criteria on the bottom.

Table 6-1. Event/Censoring Rules for EFS

Criteria	Event or Censored	Date of Event/Censoring
Relapse, no other anti-cancer therapy or prior to the start of other anti-cancer therapy, and 
 • had SCT prior to relapse, OR • no SCT prior to relapse, and days from last response assessment prior to relapse to relapse was within the following window (2 consecutive response assessments): For Group A: — ≤60 days (2 cycles (including the time waiting for	Event	Date of first relapse

count recovery) + 4 days) if didn't receive post-remission cycle
 
— <=120 days (4 cycles + 8 days) if received post-remission cycle but didn't receive ENTO mono maintenance cycle
 
— <=240 days (8 cycles + 16 days) if received ENTO mono maintenance cycle
		

For Group B:
 
— <=120 days (4 cycles + 8 days) if didn't receive maintenance cycle
 
— <= 240 days (8 cycles + 16 days) if received maintenance cycle
 
For Group C:
 
— <= 60 days (2 cycles + 4 days) if received <= 2 cycles
 
— <= 120 days (4cycles + 8 days) if received 3-4 cycles
 
— <= 240 days (8 cycles + 16 days) if received > 4 cycles
		

Treatment failure, and days from last response assessment prior to treatment failure or first dosing date, whichever is later, to treatment failure was within the window defined above
	
Event
	
Date of treatment failure

Death without treatment failure/relapse/other anti-cancer therapy, and
 
 • had SCT, OR • no SCT, and days from the date of last assessment or first dosing date, whichever is later, to the date of death was within the window defined above 	
Event
	
Date of death

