
No postbaseline assessment, no death
	
Censored
	
Date of first dose

No treatment failure/relapse/death
	
Censored
	
Date of last response assessment (and prior to other anti-cancer therapy if any) or first dosing date, whichever is later

Other anti-cancer therapy started prior to treatment failure/relapse/death	Censored	Date of last response assessment prior to other anti-cancer therapy or first dosing date, whichever is later
Days from last response assessment prior to treatment failure/relapse/death or first dosing date, whichever is later, to treatment failure/relapse/death was not within the window defined above	Censored	Date of last response assessment prior to treatment failure/relapse/death or first dosing date, whichever is later

Censoring Rules for OS:

- For a subject who is not known to have died by the end of study follow-up, OS is censored on the date the subject was last known to be alive.

For EFS or OS in months, the calculation is based on the following formula:

$$(\text{date of event/censoring} - \text{date of first dose} + 1) / 30.4375.$$

EFS and OS will be analyzed using Kaplan-Meier (KM) methods. The KM estimate of the survival function will be computed and the results will be presented using KM curves. The median will be provided along with the corresponding 95% CI. Additionally, the 25% and 75% percentiles for these endpoints will also be provided.

Follow up time for OS will be summarized as continuous variable with descriptive statistics.

- For a subject who is not known to have died by the end of study follow-up, duration of OS follow up in months = $(\text{date of last known to be alive} - \text{date of first dose} + 1) / 30.4375$
- For the remaining subjects, duration of OS follow up in months = $(\text{date of follow-up cutoff} - \text{date of first dose} + 1) / 30.4375$

Data listing for EFS and OS will be presented.

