Remission duration will be analyzed using cumulative incidence by considering competing risks. Relapse (the first situation in [Table 6-2](#)) is considered as the event of interest. Death without relapse (the second situation in [Table 6-2](#)) is a competing risk as death eliminates the occurrence of relapse. The other situations described in [Table 6-2](#) are considered as censored. There are three statuses: 0=censored, 1=relapse, and 2=death without relapse. SAS 9.4 PROC LIFETEST with statement TIME and option EVENTCODE=1 will be used. The estimates of the cumulative incidence of relapse (CIR) at 1, 3, 6, 12, 18, and 24 months (if appropriate) will be reported with the associated 95% CIs.

TTR will be summarized using descriptive statistics.

Data listing of TTR, RFS, and remission duration will be presented.

TTC will not be analyzed as data are not intensively measured/collected.

MRD rates will not be summarized as data are not measured/collected at all visits. A by-subject listing of MRD level will be provided.

The number and percentage of subjects who underwent SCT will be summarized and the corresponding 95% exact CI will be presented. In addition, the same analysis will be performed for subjects who underwent SCT at induction completion, post-remission, and maintenance completion, if applicable. A by-subject listing of SCT will be provided.

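### No scheduled or systematic recording of AML relapse after End of Study Treatment, although EFS, RFS and cumulative incidence of relapse depend on the relapse date

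*Protocol*

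**What the plan says.** **Contacts after treatment.** The protocol defines two.

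- The 30-day contact (Protocol 6.4.3) is made "to assess adverse events since the last study visit and review concomitant medications".
- Protocol 6.5 then states: "Long term follow-up for survival will be conducted every 6 months", to at most three years from the start of study therapy, with telephone contact allowed. On content: "Information to be gathered includes leukemia treatments, other malignancies, and survival". The only follow-up row in each of the six Appendix 2 tables reads "Overall survival, leukemia treatments, and other malignancies". Protocol 6.4.1 likewise says that subjects who withdraw from treatment are followed for survival.

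**Relapse visit.** Protocol 6.3.1 (Group A) says "The following procedures will be conducted at Blood Count Recovery/Remission/Relapse", and 6.3.2 and 6.3.3 have matching text for Groups B and C. These blocks sit under Treatment Assessments, and the Appendix 2 column stands before End of Study Treatment. Separately, Protocol 7.1.2.1 asks for unrelated disease progression to be entered on the eCRF, without a time limit or an assessment schedule.

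**Analysis.** EFS ends at treatment failure, AML relapse or death (Protocol 8.1.2, SAP 6.2.1). Tables 6-1 and 6-2 accept a relapse as an event if the subject "had SCT prior to relapse, OR" if it fell within a 60-, 120- or 240-day window of the previous response assessment. A separate censoring row covers "Other anti-cancer therapy started prior to treatment failure/relapse/death". For remission duration, death without relapse "is a competing risk as death eliminates the occurrence of relapse" (SAP 6.3.2).

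**The concern.** A subject who goes to transplant, completes maintenance or stops for toxicity in remission leaves study treatment while still at risk of relapse. From then on no planned contact asks whether the leukemia has come back. In Group A this exit can follow directly on induction (Protocol 3.1.2). The Group A Phase 1b table has no post-remission or maintenance phase at all, so its responders pass straight into this follow-up.

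The SAP needs the very dates that the schedule does not gather. At stake are a secondary endpoint (EFS) and the RFS and cumulative incidence of relapse (CIR) analyses. The CIR analysis is the most exposed, because it depends on separating relapse from death without relapse.

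**Working it through.** **1. What the SAP does with an unrecorded relapse** (Tables 6-1 and 6-2, SAP 6.3.2)

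| Course after treatment ends | EFS / RFS | CIR status |
|---|---|---|
| New leukemia therapy | censored at last prior response assessment | 0 |
| SCT, then death, no new therapy | event, dated at death | 2 (death without relapse) |
| No SCT, death inside gap window, no new therapy | event, dated at death | 2 |
| No SCT, death outside gap window | censored at last response assessment | 0 |
| Alive, no new therapy | censored at last response assessment | 0 |

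A recorded relapse before new therapy would be an event at its own date, status 1: always after SCT, otherwise only inside the window.

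**2. Gap windows against the follow-up interval.** The plan's windows reproduce: 2×28+4 = 60, 4×28+8 = 120, 8×28+16 = 240 days. Six months ± 4 weeks is 182.6 ± 28, about 155–211 days, longer than the first two windows.

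**3. Time without a scheduled relapse assessment.** Horizon 3×365.25 = 1,095.75 days; planned cycle lengths assumed.

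- Group A leaving after induction: day 14+14 = 28 to day 14+28+28 = 70, leaving 1,068 to 1,026 days (97% to 94%).
- Group A Phase 2, maximum planned treatment: 14+56+112+336 = 518 days, leaving 578 days (53%).
- Group B randomized, leaving after 2–4 induction cycles: day 5+56 = 61 to day 5+112 = 117, leaving 1,035 to 979 days (94% to 89%).

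**4. Illustration, with inputs that are assumptions and not in the documents.** All subjects are off treatment. Median time to relapse is 9 or 18 months, non-relapse death 15% at 12 months, and median relapse-to-death time 4 months. Half of unrecorded relapses get new therapy, and the last response assessment is 0.5 months after remission.

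True CIR at 24 months is λ/(λ+μ) × (1 − e^(−24(λ+μ))), with λ = ln 2/9 = 0.0770 or ln 2/18 = 0.0385 and μ = −ln(0.85)/12 = 0.0135. This gives 0.75 or 0.53. True RFS, e^(−24(λ+μ)), is 0.11 or 0.29.

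Simulated subjects after SCT, Table 6-2 rules applied (9 / 18 months):

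| Relapses recorded | CIR at 24 months | RFS at 24 months |
|---|---|---|
| True values | 0.75 / 0.53 | 0.11 / 0.29 |
| None | 0.00 / 0.00 | 0.13 / 0.20 |
| Half | 0.50 / 0.39 | 0.10 / 0.18 |
| All | 0.78 / 0.62 | 0.08 / 0.16 |

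- With the rules held fixed, each loss of recording lowers CIR. With none recorded, 46–48% of true relapses are coded as death and 52–54% are censored.
- With none recorded, RFS moves up in one scenario and down in the other.
- Full recording overshoots CIR, because event-free subjects are still censored at their last response assessment while later relapses count.
- Without SCT, under the 60-day window, full recording still counts only 21% / 14% of true relapses; 79% / 86% are censored.

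**The case against.** The best defence is that relapse is collected. Every Appendix 2 table has a relapse column with blood and marrow sampling, and nothing confines it to subjects on treatment. In Group A Phase 1b, which has no phase after induction, a relapse visit limited to treatment would be nearly empty. Protocol 7.1.2.1 sends progression to the eCRF without a time limit. Protocol 6.5 presents its items as included and does not call the list complete. The SAP was written from the eCRF, which is not available here, and its post-transplant row presumes that some such dates exist.

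This stands as far as it goes. A reader might infer that no relapse after treatment is recorded anywhere; the documents do not support that. They do leave collection to chance: no text extends the visit past treatment, and no later contact would trigger it.

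Three further points on the other side stand.

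- A reader might infer that the bias favours the drug. RFS moved in both directions in the illustration, overstated non-relapse death does not flatter the drug, and both randomized arms receive ENTO.
- A reader might multiply expected responders by the relapse rate in Protocol 1.1 to count missed relapses. The share that falls after treatment is nowhere given, so no count follows.
- Event-free subjects are censored at their last assessment and are not assumed to stay in remission. RFS and remission duration are exploratory, with redacted definitions.

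**Conclusion.** The point holds as a gap in ascertainment: after End of Study Treatment nothing scheduled or systematic establishes whether and when AML relapsed, while EFS, RFS and CIR need that date and the SAP counts relapse after transplant explicitly.

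Relapses that go unrecorded are censored or recast as deaths, which lowers CIR. The direction for EFS and RFS is not fixed. The size cannot be derived from the documents: it depends on how many relapses sites reported anyway, on the eCRF content, and on how many relapses fall after treatment. The 53–97% of the horizon without a scheduled assessment describes exposure to the problem, not bias. The simulated figures rest wholly on assumed inputs.

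The primary response rates, fixed at induction completion (or best response before SCT and other therapy in Group C), and OS are not affected. The point is worth acting on because the remedy is cheap.

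**What to change.** 1. Add AML relapse (yes/no, date, and basis: marrow, blood or extramedullary) to the items in Protocol 6.5 and to the follow-up row of each Appendix 2 table. State that relapse is recorded until the end of follow-up, including after SCT.
2. SAP section 1 says the study will be terminated early, so a prospective change may collect little. Query sites once, retrospectively, for every subject who left treatment in CR/CRi or PR.
3. In SAP Tables 6-1 and 6-2, count a relapse reported in follow-up as an event at its reported date. State that the 60/120/240-day window does not censor it, or show both versions. Move the censoring date of event-free subjects to the last contact at which relapse status was established; otherwise late relapses count while late relapse-free time does not.
4. Add a sensitivity analysis that treats the start of new leukemia therapy as relapse in subjects who left in remission without SCT.

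**Cost:** one data item at a contact that already takes place, one round of site queries, and an SAP revision that changes a censoring rule and so needs careful wording. No visit or marrow is added. The SAP is to be final before database finalization; a later change belongs in the CSR. The downside is that relapse dates from routine care are less exact than those from scheduled marrows.
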